Appendix 2 List of Permitted and Prohibited Prior/Concomitant Medications

Prohibited medications are shown in [Listing 1](#), [Listing 2](#), [Listing 3](#), [Listing 4](#), [Listing 5](#), and [Listing 6](#). Medications permitted with restrictions are listed in [Listing 7](#), [Listing 8](#), and [Listing 9](#). **These may not be all-inclusive listings.** Please contact the medical monitor(s) if the investigators have any questions or concerns regarding any medication not listed that your subjects may be taking before enrollment or start during the course of the E2609-G000-202 study.

Antibiotics, analgesics, and anti-inflammatory drugs intended for short courses of treatment are permitted and do not need to follow the restrictions of [Listing 9](#) for a stable dose of 4 weeks before Baseline. If these medications may affect cognitive function but the medications are clinically indicated, then cognitive testing should not take place until at least 72 hours after the last dose of the course of treatment.

Prohibited Prior/Concomitant Medications

Listing 1 Drugs with High Risk of Torsades de Pointes or QTc Prolongation

| Generic name | Brand name (Names shown are not exhaustive and are examples only; names may be the ® or ™) | Comments |
|---|--|---|
| Prohibited from 14 days (or 5 half-lives, whichever is longer) before Randomization until after the last treatment visit | | |
| Anti-arrhythmic/ abnormal heart rhythm | | |
| Amiodarone | Cordarone; Pacerone | Incidence in females greater than males, Torsades de Pointes risk regarded as low |
| Disopyramide | Norpace | Incidence in females greater than males |
| Dofetilide | Tikosyn | |
| Ibutilide | Corvert | Incidence in females greater than males |
| Procainamide | Pronestyl; Procan | |
| Quinidine | Cardioquin; Quinaglute | Incidence in females greater than males |
| Sotalol | Betapace | Incidence in females greater than males |
| Antihistamine/ allergic rhinitis | | |
| Astemizole | Hismanal | No longer available in United States |
| Terfenadine | Seldane | No longer available in United States |
| Anti-anginal/ heart pain | | |
| Bepridil | Vascor | Incidence in females greater than males |
| Antibiotic/ bacterial infection | | |
| Clarithromycin | Blaxin | |
| Moxifloxacin | Avelox | |
| Sparfloxacin | Zagam | |
| Listing 1 continued | | |
| Antimalarial/ malaria infection | | |
| Chloroquine | Aralen | |
| Halofantrine | Halfan | Incidence in females greater than males |
| Antipsychotic/ anti-emetic/ schizophrenia/ nausea | | |
| Chlorpromazine | Thorazine | |
| Gastrointestinal stimulant/ heartburn | | |
| Cisapride | Propulsid | |
| Antinausea/ nausea | | |

Listing 1 Drugs with High Risk of Torsades de Pointes or QTc Prolongation

| Generic name | Brand name (Names shown are not exhaustive and are examples only; names may be the ® or ™) | Comments |
|--|--|---|
| Domperidone | Motillum | Not available in the United States |
| Sedative; antinausea/ anesthesia adjunct, nausea | | |
| Droperidol | Inapsine | |
| Antibiotic; gastrointestinal stimulant/ bacterial infection; increase gastrointestinal motility | | |
| Erythromycin | Erythrocin; E.E.S. | Incidence in females greater than males |
| Antipsychotic/ schizophrenia | | |
| Haloperidol | Haldol | When given intravenously or at higher than recommended doses, risk of sudden death, QT prolongation, and torsades increases |
| Mesoridazine | Serentil | |
| Thioridazine | Mellaril | |
| Opiate agonist/ pain control, narcotic dependence | | |
| Levomethadyl | Orlaam | |
| Methadone | Methadose; Dolophine | Incidence in females greater than males |
| Anti-infective/ pneumocystis pneumonia | | |
| Pentamidine | Pentam; NebuPent | Incidence in females greater than males |
| Antipsychotic/ Tourette's tics | | |
| Pimozide | Orap | Incidence in females greater than males |
| Antilipemic/ hypercholesterolemia | | |
| Probucol | Lorelco | No longer available in United States |
| Anticancer | | |
| Arsenic trioxide | Trisenox | Used for leukemia |
| Vandetanib | Zactima | Used for thyroid cancer |

Note: This list is not exhaustive.

QTc = Corrected QT interval.

Listing 2 Prohibited Medications Within 7 Days (or 5 Half-lives, Whichever is Longer) Before Randomization and Until after the Last Treatment Visit)

| Generic Name | Brand name (Names shown are not exhaustive and are examples only; names may be the ® or ™) |
|---|---|
| Anticoagulants | |
| Adeporin | Normiflo |
| Alteplase, tPA | Activase, Cathflo Activase |
| Anisindione | Miradon |
| Antithrombin III | ATryn, Thrombate III |
| Argatroban | Argatroban |
| Bivalirudin | Angiomax |
| Dabigatran | Pradaxa |
| Dalteparin | Fragmin |
| Danaparoid | Orgaran |
| Dicumarol | Dicumarol |
| Enoxaparin | Lovenox |
| Fondaparinux | Arixtra |
| Heparin Sodium | Monoject |
| Lanoteplase | Lanoplase |
| Lepirudin | Refludan |
| Pentosan polysulfate sodium | Elmiron |
| Reteplase | Retavase, Retevase |
| Staphylokinase | Eskinase, Heberkinasa Kabikinase, Streptase, Thrombosolv, Zykinase |
| Streptokinase | Streptase |
| Tenecteplase | TNKase |
| Tinzaparin | Innohep |
| Urokinase | Abbokinase, Kinlytic |
| Warfarin | Coumadin, Jantoven |
| Antiplatelet drugs | |
| Aspirin and Plavix (revised per Amendment 01) | 
For subjects who consent to CSF sample collection: Aspirin or clopidogrel is permitted in all subjects. Aspirin and clopidogrel in combination is not permitted. (revised per Amendments 01 and 02)
 
For subjects who do not consent to CSF sample collection: Aspirin and clopidogrel, individually or in combination, is permitted. (revised per Amendment 02)
 |

Note: This list is not exhaustive.

Listing 3 Prohibited Medications Within 5 Half Lives or 60 Days, Whichever is Longer, Before Randomization and Until after the Last Treatment Visit

| Generic name | Brand name (Names shown are not exhaustive and are examples only; names may be the ® or ™) |
|---|--|
| Systemic Immunosuppressants^a and Immunomodulatory therapy | |
| Azathioprine | Azasan, Imur |
| Ciclosporine | Gengraf, Neoral |
| Dexamethasone | Decadron, Dexasone, Diodex, Hexadrol, Maxidex |
| Fingolimod | Gilenya |
| Methotrexate | Trexall |
| Methylprednisolone | Medrol, Meprolone |
| Mycophenolate | CellCept, Myfortic |
| Prednisolone | Deltasone, Prednicot, Prednisone Intensol, Rayos, Sterapred, Sterapred DS |

Note: This list is not exhaustive.

a: Topical and inhaled formulations with minimal systemic exposure need not be prohibited.

Listing 4 Prohibited Medications Within 6 Months Before Randomization

| Generic name | Brand name (Names shown are not exhaustive and are examples only; names may be the [®] or [™]) |
|---|---|
| Immunoglobulin therapy | |
| Adalimumab | Humira |
| Bevacizumab | Avastin |
| Efalizumab | Raptiva |
| Etanercept | Enbrel |
| Immune globulin IV, IVIG, IGIV | Carimune, Flebogamma, Gamimune N, Gammagard, Gamunex, Gammar-P IV, Iveegam, Octagam, Panglobulin, Vigam, Polygam S/D, Privigen, Sandoglobulin, Venoglobulin-S |
| Infliximab | Remicade |
| Omalizumab | Xolair |
| Ranibizumab | Lucentis |
| Other monoclonal antibodies not listed here | |

Note: This list is not exhaustive.

Listing 5 Prohibited Live Vaccines Within 3 Months Before Randomization Until after the Last Treatment Visit (this does not apply to non-live/inactivated vaccines)

| Bacterial vaccines | Viral vaccines |
|---|---|
| Bacillus Calmette-Guérin vaccine against tuberculosis | Measles vaccination |
| Cholera vaccination (oral) | Rubella vaccination |
| | Oral polio vaccination (Sabin) |
| | Yellow fever vaccination |
| | Varicella (chickenpox) vaccination |
| | Rotavirus vaccination |
| | Japanese encephalitis vaccination |
| | Live attenuated influenza vaccine (FluMist, Fluenz) |
| Typhoid vaccination (oral) | Mumps vaccination |

Note: This list is not exhaustive

**Listing 6 Strong CYP3A4 Inhibitors Prohibited Within 5 Half-Lives or 14 Days
(Whichever Is Longer) Before Randomization Until After the Last Treatment Visit**

| Generic name | Brand name(s) |
|---------------------|--|
| boceprevir | Victrelis |
| clarithromycin | Clarithromycin, clarithromycin extended release, Prevpac |
| cobicistat | Tybost, Stribild, |
| conivaptan | Vaprisol |
| danoprevir | |
| elvitegravir | Vitekta, Stribild |
| indinavir | Crixivan |
| itraconazole | Sporanox, Onmel |
| ketoconazole | Xolegel, Nizoral, Ketodan |
| lopinavir | Kaletra |
| nefazodone | Serzone |
| nelfinavir | Viracept |
| posaconazole | Noxafil |
| ritonavir | Norvir, Kaletra |
| saquinavir | Invirase, Fortovase |
| telaprevir | Incivek |
| telithromycin | Ketek |
| tipranavir | Aptivus |
| troleandomycin | Triocetin |
| voriconazole | Vfend, Voriconazole |

Note: This list is not exhaustive

Permitted Prior/Concomitant Medications

Listing 7 Medications Which Need To Be on a Stable Dose for 12 Weeks Before the Baseline Cognitive Assessments at Visit 2 and Remain on the Same Stable Dose from Baseline to Follow-Up Visit 2

| Generic name | Brand name (Names shown are not exhaustive and are examples only; names may be the ® or ™) |
|----------------------------|--|
| Cognitive Enhancers | |
| Donepezil | Aricept |
| Galantamine | Reminyl |
| Memantine | Namenda |
| Rivastigmine | Exelon |

Note: This list is not exhaustive.

Listing 8 Permitted Medications Used on PRN Basis Which are Not to be Used Within 72 Hours before Cognitive Testing

| Generic name | Brand name (Names shown are not exhaustive and are examples only; names may be the ® or ™) |
|---|---|
| Opiates | |
| Morphine | Astramorph PF, Avinza, Depo Dur, Duramorph, Infumorph, Kadian, MS Contin, MSIR, Oramorph SR, RMS, Roxanol |
| Opiate Agonists | |
| Codeine | Codeine |
| Fentanyl | Actiq, Duragesic, Fentora, Onsolis, Sublimaze |
| Meperidine | Demerol, Meperitab |
| Oxycodone | Dazidox, Endocodone, Eth-OxyDose, OxyContin, OxyFast, OxyIR, Percolone, Roxicodone, Roxicodone Intensol |
| Other opioids or opioid agonists which are used on PRN basis | |
| Benzodiazepines and sedatives | |
| Alprazolam | Alprazolam Intensol, Niravam, Xanax |
| Amitriptyline | (various) |
| Chlordiazepoxide | H-Tran, Librium |
| Clonazepam | Ceberclon, Klonopin |
| Diazepam | Diastat, Dizac, Valium |
| Dothiepin | (various) |
| Estazolam | ProSom |
| Flunitrazepam | Rohypnol |
| Flurazepam | Dalmane |
| Lorazepam | Ativan |
| Midazolam | Versed |
| Olanzapine | Zyprexa |
| Promethazine | Phenergan; others |
| Ramelteon | Rozerem |
| Risperidone | Risperdal |
| Temazepam | Restoril |
| Triazolam | Halcion |
| Zolpidem | Ambien; others |
| Zopiclone | (various) |
| Other benzodiazepines, tricyclic antidepressants, antipsychotics and other drugs which are used on PRN basis as sedatives | |

Note: This list is not exhaustive

PRN = Pro re nata

Listing 9 Permitted Centrally Active or Psychiatric Medications

| Generic Name | Brand name (Names shown are not exhaustive and are examples only; names may be the ® or ™) |
|--|--|
| If to be used on a PRN basis see Listing 8 . If to be used chronically, subjects must be on a stable dose for ≥4 weeks before Baseline. Changes in dose or initiation of new concomitant medications for chronic use (not PRN use) is permitted but if the medication affects cognitive function, do not conduct cognitive testing until the dose is stable for 4 weeks. | |
| Antidepressants | |
| Amitriptyline hydrochloride | Elavil |
| Amoxapine | Amoxapine |
| Bupropion | Aplenzin, Budeprion, Buproban, Zyban, Wellbutrin |
| Citalopram | Celexa |
| Clomipramine hydrochloride | Anafranil |
| Desipramine hydrochloride | Norpramin |
| Desvenlafaxine | Pristiq |
| Doxepin hydrochloride | Prudoxin, Silenor, Sinequan, Zonalon |
| Duloxetine | Cymbalta |
| Escitalopram | Lexapro |
| Fluoxetine | Prozac, Sarafem, Selfemra |
| Fluvoxamine | Luvox |
| Imipramine hydrochloride | Tofranil |
| Isocarboxazid | Marplan |
| Maprotiline hydrochloride | Ludomil |
| Mirtazapine | Remeron Soltab |
| Nortriptyline hydrochloride | Aventyl, Pamelor |
| Paroxetine | Paxil, Pexeva |
| Phenelzine | Nardil |
| Protriptyline hydrochloride | Vivactil |
| Rasagiline | Azilect |
| Selegiline | EMSAM |
| Sertraline | Sertaraline, Zoloft |
| Tranlycypromine | Parnate |
| Trazodone hydrochloride | Desyrel, Oleptro |
| Trimipramine maleate | Surmontil |
| Venlafaxine hydrochloride | Effexor |

Listing 9 Permitted Centrally Active or Psychiatric Medications

| Generic Name | Brand name (Names shown are not exhaustive and are examples only; names may be the ® or ™) |
|---|--|
| Mood Stabilizers (Listing 8 continued) | |
| Carbamazepine | Carbatrol, Epitol, Equetro, Tegretol, Tegretol XR |
| Lamotrigine | Lamictal, Lamictal CD, Lamictal ODT, Lamictal XR |
| Valproic acid | Depacon, Depakene, Depakote, Depakote ER, Divalproex Sodium, Stavzor, Valproate |
| Antipsychotics | |
| Acetophenazine | Tindal |
| Aripiprazole | Abilify |
| Asenapine | Saphris |
| Olanzapine | Zyprexa |
| Chlorpromazine | Thorazine |
| Haloperidol | Haloperidol, Haldol |
| Clozapine | Clozaril, Fazaclo |
| Fluphenazine | Prolixin |
| L-Methylfolate | Deplin, L-Methylfolate Calcium |
| Loxapine | Loxitane |
| Mesoridazine | Serentil |
| Perphenazine | Trilafon |
| Quetiapine | Seroquel |
| Risperidone | Risperdal |
| Thioridazine | Mellaril |
| Thiothixene | Navane |
| Trifluoperazine | Stelazine |
| Benzodiazepines | |
| Alprazolam | Alprazolam Intensol, Niravam, Xanax |
| Chlordiazepoxide | H-Tran, Librium |
| Clonazepam | Ceberclon, Klonopin |
| Diazepam | Diastat, Dizac, Valium |
| Estazolam | ProSom |
| Flunitrazepam | Rohypnol |

Listing 9 Permitted Centrally Active or Psychiatric Medications

| Generic Name | Brand name (Names shown are not exhaustive and are examples only; names may be the ® or ™) |
|--------------|--|
| Flurazepam | Dalmane |
| Lorazepam | Ativan |
| Midazolam | Versed |
| Temazepam | Restoril |
| Triazolam | Halcion |
| Zopiclone | Imovane, Zimovane |
| Zopidem | Ambien, Ambien CR, Intermezzo, Stilnox, Stilnoct, Sublinox, Hypnogen, Zolsana |

Note: This list is not exhaustive.

PRN = Pro re nata

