9.4.7 Prior and Concomitant Therapy

Medication (including over-the-counter medications) or therapy administered to the subject before the study (within 6 months of randomization) and during the study (starting at the date of informed consent) will be recorded on the Prior & Concomitant Medication eCRF or Non-Pharmacological Procedures eCRF. The investigator will record on the Adverse Event eCRF any AE for which the concomitant medication/therapy was administered. If the concomitant medication/therapy is being administered for a medical condition present at the time of entry into the study, the investigator will record the medical condition on the Medical History and Current Medical Condition eCRF.

Listings of prohibited and permitted drugs are provided in [Appendix 2](#). Prohibited medications are presented in [Listing 1](#), [Listing 2](#), [Listing 3](#), [Listing 4](#), [Listing 5](#), and [Listing 6](#). Medications that are permitted with restrictions are listed in [Listing 7](#), [Listing 8](#), and [Listing 9](#).

The following agents are not permitted before randomization (specific timeframes are shown below) and throughout the study until after the last treatment visit:

- Anticoagulants (eg, warfarin, digabatin) are not permitted for a period of 5 half-lives or 7 days (whichever is longer) before randomization
- Drugs which may cause QTc prolongation are not permitted for a period of 5 half-lives or 14 days (whichever is longer) before randomization
- Strong CYP3A4 inhibitors are not permitted for a period of 5 half-lives or 14 days (whichever is longer) before randomization
- Live vaccines are not permitted within 3 months before randomization. This does not apply to non-live/inactivated vaccines
- Ig therapy and biologic drugs are not permitted within 6 months before randomization
- Systemic or ocular immunosuppressive or immunomodulatory drugs are not permitted for a period of 5 half-lives or 60 days (whichever is longer) before randomization

Subjects taking AChEIs or memantine must meet the following criteria in order to be included in the primary analyses:

- On a stable dose for 12 weeks before the Baseline cognitive assessments at Visit 2
- Remain on a stable dose while on study

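### Appendix 2 lists four antipsychotics as permitted (Listing 9) that it also prohibits for QTc/torsades risk (Listing 1), with no rule on which listing prevails

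*Protocol*

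**What the plan says.** Section 9.4.7 (Prior and Concomitant Therapy) bars QTc-prolonging drugs as a class, before randomization and throughout treatment. For names it refers the site onward: "Listings of prohibited and permitted drugs are provided in" Appendix 2. The introduction to that appendix assigns Listings 1 to 6 to prohibited drugs and Listings 7 to 9 to drugs permitted with restrictions.

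- **Listing 1** (high risk of torsades or QTc prolongation) applies this window to every drug in it: "Prohibited from 14 days (or 5 half-lives, whichever is longer) before Randomization until after the last treatment visit". Chlorpromazine, haloperidol, mesoridazine and thioridazine are among its entries.
- **Listing 9** (permitted centrally active or psychiatric drugs) names the same four under Antipsychotics, for example "Haloperidol | Haloperidol, Haldol" and "Thioridazine | Mellaril"; the thioridazine row reads the same in Listing 1. For chronic use, its head note says "subjects must be on a stable dose for ≥4 weeks before Baseline", and it adds: "Changes in dose or initiation of new concomitant medications for chronic use (not PRN use) is permitted". The one further condition there concerns cognition: for a drug that affects it, cognitive testing waits until the dose has been stable for 4 weeks.

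The appendix introduction also tells sites: "Please contact the medical monitor(s) if the investigators have any questions or concerns regarding any medication not listed".

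**The concern.** The same drug cannot be both permitted for chronic use and banned throughout treatment. Sites look up individual drug names in Appendix 2, and for these four the answer depends on which table they open.

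A site that checks only Listing 9 could enrol a subject who is stable on one of these drugs, or start one during the study. The first would be an eligibility violation. Both would expose a subject to a drug that the protocol itself classes as high risk for torsades or QTc prolongation. Section 7.1 gives some reason for care: the 800 mg single dose of E2609 was associated with a QTcF increase of 14.9 msec. That dose is 800/50 = 16 times the highest dose here, so it does not show an effect at 50 mg.

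**Working it through.** No sample size, power or alpha figure is involved. The check compares the listings, then asks which text governs and what would catch an error.

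**1. Overlap of named drugs**

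| Drug | Listing 1 (prohibited) | Listing 9 (permitted) |
|---|---|---|
| Chlorpromazine | yes | yes |
| Haloperidol | yes | yes |
| Mesoridazine | yes | yes |
| Thioridazine | yes | yes |
| Pimozide | yes | no |

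- Listing 1 names 30 drugs, 5 of them under an antipsychotic heading (the five above). Listing 9 has 17 entries under Antipsychotics.
- The overlap is 4: 4/30 of Listing 1, 4/5 of its antipsychotics and 4/17 of the Listing 9 antipsychotics.
- No other drug named in Listing 1 or Listing 6 is named in Listings 7, 8 or 9.
- Listing 8 also has catch-all entries for other opioids and for other antipsychotics used as needed. Neither excludes Listing 1 drugs, and methadone and levomethadyl are in Listing 1.

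**2. Can both rules be met?** Listing 9 requires at least 4 × 7 = 28 days of stable dosing before Baseline. Listing 1 requires no dosing for at least 14 days before randomization and none until after the last treatment visit. A subject who continues the drug cannot satisfy both, and one who starts it during treatment breaches Listing 1 at once.

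**3. Does route or dose separate the entries?** No. Listing 1 comments on haloperidol: "When given intravenously or at higher than recommended doses, risk of sudden death, QT prolongation, and torsades increases". That says when the risk rises; it does not confine the ban to those uses. Listing 9 gives no route or dose limit either.

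**4. Which text governs?** Section 9.4.7 limits the stable-dose permission to drugs that are not prohibited, and puts the same limit on starting or adjusting a drug during the study. Exclusion criterion 25 covers use of QT-prolonging medication, and criterion 37 covers breaches of the medication restrictions. All agree that the ban prevails.

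**5. Does Appendix 2 say so?** No. Neither its introduction nor the notes to Listings 1 and 9 give an order of precedence. The medical-monitor instruction concerns drugs that are not listed, so it does not reach a drug listed twice.

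**6. What would catch an on-study start?** Table 7 schedules treatment-period ECGs at Visits 5, 7, 9, 11, 14, 16 and 18, that is weeks 2, 4, 8, 12, 26, 52 and 78. The intervals are 2, 4, 4, 14, 26 and 26 weeks, so the longest is 26. Concomitant medication is reviewed at every visit from Visit 4. After week 26 those visits fall at weeks 39, 52, 65 and 78, so the longest gap between reviews is 13 weeks.

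**The case against.** The strongest reply is that the protocol already resolves the conflict and that the failure route is narrow. Note j to Table 7 sends sites, for concomitant medication, to Section 9.4.7 and not straight to Listing 9. That section carries the ban and limits every permission to drugs that are not prohibited; the synopsis repeats this. Criterion 25 should exclude a chronic user whatever Listing 9 says, and criterion 6 may remove some subjects with psychotic symptoms. Medication reviews come at most 13 weeks apart, unscheduled ECGs are available, and the QTcF stopping rules in Section 9.3.3 apply. On this view it is a minor drafting slip in an appendix.

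Much of that stands. The governing rule can be recovered, and the harm is limited. But Section 9.4.7 bars QTc drugs only as a class and leaves the names to Appendix 2, where the two listings disagree. The QTc entry criterion is applied at Screening or Baseline, so it does not screen later starts. The stopping rules act only once an ECG has been taken. A medication review helps only if the reviewer does not consult Listing 9 and find the drug permitted.

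It is also fair to say that deleting the four rows would not be enough, because the catch-all entries in Listing 8 would remain. That is why the fix includes a precedence sentence.

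**Conclusion.** The point holds. It is an internal inconsistency, and Listing 9 is the text in error. Four drugs are named as both prohibited and permitted, and Appendix 2 gives no means of resolving the conflict. It should be fixed because it leaves a wrong operational safety instruction in the tables that sites use to look up drug names.

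The consequence is confined to subject safety and eligibility. No endpoint, sample size or analysis is affected. The 26-week figure is the longest nominal interval between scheduled ECGs; it ignores visit windows and unscheduled recordings. How many subjects might be affected cannot be derived from the protocol. Any harm requires a site to rely on Listing 9 without applying Section 9.4.7.

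**What to change.** 1. Delete chlorpromazine, haloperidol, mesoridazine and thioridazine from Listing 9.
2. Add one sentence at the head of Appendix 2: a drug covered by Listings 1 to 6 is prohibited even if it is named in, or falls within a class entry of, Listings 7 to 9. This repeats the rule already in Section 9.4.7 and also closes the Listing 8 catch-all entries.
3. Notify sites by letter.

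The sponsor has made a similar edit before. The revision history for Version 2.0 records that nefazodone was moved from Listing 9 to Listing 6 because it is a strong CYP3A4 inhibitor. The log does not show that it was ever in both lists, so this is a precedent for the type of edit only.

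The cost is four rows, one sentence and a site letter. Design, sample size and analysis are unchanged.
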